#### **4.2.4 Laboratory Values**

Laboratory values below the lower level of quantification (Q) that are reported as "<Q" or "≤Q" in the database will be imputed by  $Q \times 0.99$  for analysis purposes. However, the original value will be reported in the listings.

Laboratory values above the upper level of quantification (Q) that are reported as “>Q” or “≥Q” in the database will be imputed by  $Q \times 1.01$  for analysis purposes. However, the original value will be reported in the listings.

### **4.3 Software**

Sample size calculation was performed using East 6 (Version 6.3.1). Statistical analyses and data summary will be conducted using SAS Version 9.4 or higher.

## **5 STUDY POPULATION SUMMARIES**

### **5.1 Study Disposition**

Enrollment for subjects randomized will be summarized by region, country, and study center. Subject disposition will be summarized categorically and will include the number and percentage of subjects in each analysis population. Subject disposition data including subject status on treatment, subject status on the study, time on study, and time from randomization to first dose will be summarized by treatment arm.

### **5.2 Protocol Deviations**

Number and percentage of subjects with important protocol deviations (IPDs) after randomization will be summarized by treatment arm. A listing of subjects with IPDs will be produced. IPD categories, subcategory codes, and descriptions will be defined by sponsor IPD guidance and used during the course of the study. The sponsor will review IPDs throughout the study prior to database lock. The final IPD list will be used to produce the IPD summary table and listing.

### **5.3 Demographics and Baseline**

#### **5.3.1 Demographics and Baseline Characteristics**

The following demographic and baseline characteristics will be summarized:

- Age at informed consent (continuous)
- Age category (< 65, ≥ 65; <70 vs. ≥70; < 75, ≥ 75)
- Sex (male, female)
- Race

- Ethnicity
- Height (cm)
- Weight (kg)
- Body surface area (m^2), calculated as  $\sqrt{\text{height (cm)} * \text{weight (kg)}/3600}$
- ECOG performance status (2 vs ≤1)
- Region (North America, Western Europe, Central and Eastern Europe, Asia Pacific)

### 5.3.2 Baseline Disease Characteristics

The following baseline disease characteristics will be summarized:

- Time (months) from initial diagnosis to randomization
  - Time (months) from prior treatment to randomization
  - Bulky disease (<5 cm, ≥5 cm; <10 cm, ≥10 cm)
  - Rai stage (0, I, II, III, and IV)
  - Binet Stage (A, B, and C)
  - 17p del and/or 11q del (yes, no)
  - 17p del (yes, no)
  - 11q del (yes, no)
  - TP53 mutation (mutated, unmutated)
  - Immunoglobulin heavy-chain variable (IGHV; mutated, unmutated)
  - Complex karyotype (yes, no)
  - β2-microglobulin (mg/L) group at baseline (≤3.5 mg/L, >3.5 mg/L)
  - High risk features:
    - 17p del and 11q del (yes, no)
    - 17p del and/or TP53 mutation (yes, no)
    - 17p del and TP53 mutation (yes, no)
    - 17p del and 11q del and TP53 mutation (yes, no)
    - 17p del and unmutated IGHV (yes, no)
    - 17p del and complex karyotype (yes, no)
    - 11q del and complex karyotype (yes, no)
  - Cytopenia at baseline
    - Neutropenia - ANC ≤1.5 x 10^9/L (yes, no)
    - Anemia - Hgb ≤11 g/dL (yes, no)
    - Thrombocytopenia - platelet counts ≤100 x 10^9/L (yes, no)
    - Any of the above (yes, no)
    - All of the above (yes, no)
-

- Prior red blood cell (RBC) transfusion within 28 days before randomization
- Prior platelet transfusion within 28 days before randomization
- Constitutional symptoms (weight loss, fever, night sweats, fatigue)
- Creatinine clearance (mL/min)
- Absolute lymphocyte counts ( $10^9/L$ )
- Absolute neutrophil count ( $10^9/L$ )
- Platelet count ( $10^9/L$ )
- Hemoglobin level (g/dL)

### **5.3.3 Randomization Stratification Factors**

Randomization stratification factors per IWRS recording will be summarized individually and as cross-tabulation:

- Presence of 17p del (yes, no)
- ECOG performance status (ECOG = 2 versus ECOG  $\leq 1$ )
- Number of prior therapies (1-3 versus  $\geq 4$ )

### **5.4 Medical History**

General medical history data will be coded per Medical Dictionary for Regulatory Activities (MedDRA), summarized by system organ class and preferred term, and presented as a data listing.

## **6 TREATMENTS AND MEDICATIONS**

Medications recorded on the electronic case report forms (eCRFs) will be coded using the World Health Organization (WHO) Drug Dictionary.

### **6.1 Prior and Concomitant Medications**

Prior and concomitant medications will be summarized by Anatomical Therapeutic Chemical (ATC) Class text and WHO Drug base substance preferred name. Each subject will be counted only once for each therapeutic class, each generic name, and overall.

### **6.2 Prior and Subsequent Anticancer Therapies**

Prior and subsequent anticancer therapy used to treat CLL will be coded and summarized based on line of therapy and type of therapy. Each subject will be counted only once for each line and type of therapy and overall.

### 6.3 Study Treatment Exposure

Study treatment exposure will be summarized by as follows:

- Duration of exposure (months):  $(\text{last dose date} - \text{first dose date} + 1) / 30.4375$
- Average daily dose (mg): calculated as  $(\text{total dose received [mg]} / \text{duration of exposure [days]})$
- Relative dose intensity: calculated as  $(\text{total cumulative dose received [mg]} / (\text{duration of exposure [days]} * 100 [\text{mg}] * 2) * 100)$

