6.2.4 Dose Modification and Discontinuation for Acalabrutinib

Treatment-related Lymphocytosis

Treatment-related lymphocytosis is defined as ALC > 5000/ μ L and an increase above baseline, and is associated with agents known to inhibit BCR ([Hallek 2008](#), [NCCN Version 1.2016](#),

[Cheson 2012](#)). Given the known mechanism of action of BCR-inhibiting agents including ibrutinib, treatment-related lymphocytosis is an expected and frequent phenomenon observed with initiation (or re-initiation) of Btk inhibitors. Specifically, the IMBRUVICA approved label states an increase in lymphocyte counts ($\geq 50\%$ increase from baseline and above absolute lymphocyte count of $5,000/\mu\text{L}$) occurred in 77% of subjects (N=195) in the pivotal Phase 3 CLL study. The onset of lymphocytosis occurred during the first month of ibrutinib therapy and resolved by a median of 23 weeks (range: 1 to 104+ weeks). Asymptomatic treatment-related lymphocytosis should not be considered an AE and subjects should remain on study treatment. A high number of circulating malignant cells ($\geq 400,000/\mu\text{L}$) may confer increased risk; these subjects should be closely monitored. Administer supportive care such as hydration and/or leukaphoresis as indicated. Acalabrutinib may be temporarily held and the Medical Monitor should be contacted.

The actions in [Table 6-1](#) should be taken for the following toxicities:

- Grade 4 ANC ($< 500/\mu\text{L}$) for > 7 days (Neutrophil growth factors are permitted per ASCO guidelines [[Smith 2015](#)] and use must be recorded on the case report form [CRF]).
- Grade 3 platelet decreases in presence of significant bleeding.
- Grade 4 platelet decreases.
- Grade 3 or 4 nausea, vomiting, or diarrhea, if persistent despite optimal antiemetic and/or anti-diarrheal therapy.
- Any other Grade 4 toxicity or unmanageable Grade 3 toxicity.

Table 6-1. Drug Discontinuation Actions for Acalabrutinib

Occurrence	Action
1st - 2nd	Hold acalabrutinib until recovery to Grade ≤ 1 or baseline; may restart at original dose level
3rd	Hold acalabrutinib until recovery to Grade ≤ 1 or baseline; restart at one dose level lower (100 mg once daily)
4th	Discontinue acalabrutinib

Any changes to the dosing regimen must be recorded in the Dosage Administration CRF.

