6.2.9 Dose Modification and Discontinuation for Ibrutinib

The actions in [Table 6-2](#) should be taken for the following toxicities:

- Grade 4 ANC (< 500/ μ L) for > 7 days (Neutrophil growth factors are permitted per ASCO guidelines [[Smith 2015](#)] and use must be recorded on the CRF).
- Grade 3 platelet decreases in presence of significant bleeding.
- Grade 4 platelet decreases.
- Grade 3 or 4 nausea, vomiting, or diarrhea, if persistent despite optimal antiemetic and/or anti-diarrheal therapy
- Any other Grade 4 toxicity or unmanageable Grade 3 toxicity.

Table 6-2. Dose Discontinuation Actions for Ibrutinib

Occurrence	Action
1st	Hold ibrutinib until recovery to Grade \leq 1 or baseline; may restart at original dose level (420 mg daily)
2nd	Hold ibrutinib until recovery to Grade \leq 1 or baseline; may restart at 280 mg daily
3rd	Hold ibrutinib until recovery to Grade \leq 1 or baseline; may restart at 140 mg daily
4th	Discontinue ibrutinib

Any changes to the dosing regimen must be recorded in the Dosage Administration CRF.

Note: If local regulations require following local prescribing information for dose modifications/discontinuation, and they differ from the aforementioned, then the local regulations should be followed.

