## 2 STUDY DESCRIPTION

### 2.1 Study Design

This randomized, multicenter (ie, approximately 200 global centers), open-label, non-inferiority Phase 3 study is designed to evaluate the efficacy and safety of acalabrutinib (ACP-196) versus ibrutinib in subjects with relapsed or refractory chronic lymphocytic leukemia (CLL) who have high-risk prognostic markers (eg, 17p del and/or 11q del) per National Comprehensive Cancer Network (NCCN) guidelines ([NCCN Version 1. 2016](#)).

Approximately 500 eligible subjects will be randomized in a 1:1 ratio into 2 arms to receive either acalabrutinib 100 mg BID (Arm A; N=250) or ibrutinib 420 mg QD (Arm B; N=250).

This study will use an Interactive Web Response System (IWRS) for randomization. Randomization will be used to minimize bias in the assignment of subjects to treatment groups, to increase the likelihood that known and unknown subject attributes (eg, demographic and baseline characteristics) are evenly balanced, and to enhance the validity of statistical comparisons across treatment groups.

Randomization will be performed stratified by the following factors:

- Presence of 17p del
- Eastern Cooperative Oncology Group (ECOG) performance status (ECOG = 2 versus ECOG ≤1)

- Number of prior therapies (1-3 versus  $\geq 4$ )

An independent DMC will be formed and constituted according to regulatory agency guidelines. Detailed information regarding the composition of the DMC and detailed DMC procedures will be provided in a separate charter. The DMC will review the safety data periodically and provide recommendations according to the charter.

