### 3.3 Per Protocol Population

The per protocol (PP) population includes subjects in the ITT population with exclusion of:

- Subjects with < 75% relative dose intensity.
- Violated protocol inclusion or exclusion criteria that may affect interpretation of efficacy (Inclusion Criteria #3, #5, #6, Exclusion Criteria #2-4 and #6-9 in Protocol Amendment 5 dated 21 Oct 2020, and Inclusion Criterion #7 from Protocol Amendment 4 dated 14 Dec 2017).
- Received the incorrect treatment for  $\geq 7$  days.

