### 6.4 Study Treatment Modifications

For subjects randomized to acalabrutinib arm, acalabrutinib dose withholding is defined as missing dose for  $\geq 7$  consecutive days, and acalabrutinib dose reduction is defined as taking lower dose level (100 mg QD) for  $\geq 3$  consecutive days. Subjects with dose withholding and reduction will be summarized by percent of subjects as well as descriptive statistics.

For subjects randomized to ibrutinib, dose delay and modifications are defined the same as acalabrutinib and will be summarized by percentage of subjects and by descriptive statistics.

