### 7.1.3 Sensitivity Analyses

The following sensitivity analyses will be performed for PFS as assessed by IRC between acalabrutinib and ibrutinib in support of primary efficacy analyses:

- Unstratified analyses
- The PFS will be analyzed as the time from date of randomization to the date of first IRC-assessed disease progression or death due to any cause, whichever comes first, regardless of the use of subsequent anticancer therapy; i.e., subjects will not be censored at the last adequate IRC assessment prior to the subsequent anticancer therapy
- Subjects with PFS events after 2 or more consecutively missed visits will not be censored at the last adequate assessment. In particular, IRC-confirmed progressive disease or death after 2 or more consecutively missed visits will be included as a PFS event
- Analysis using per protocol population

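### Relative dose intensity is defined only against acalabrutinib's 200 mg/day, so the 75% per-protocol cut-off falls at 75% of planned dose for acalabrutinib but 35.7% for ibrutinib

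*SAP*

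**What the plan says.** SAP 6.3 opens with "Study treatment exposure will be summarized by as follows" and lists duration of exposure, average daily dose and RDI. RDI is cumulative dose divided by a quantity ending "duration of exposure [days]} * 100 [\text{mg}] * 2) * 100": days times 100 mg times 2, expressed as a percentage. The section names no arm, and SAP 4 makes summaries by treatment arm the default.

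SAP 3.3 removes from the per-protocol population "Subjects with < 75% relative dose intensity", again without naming an arm. SAP 7.1.3 lists "Analysis using per protocol population" among four sensitivity analyses of IRC-assessed PFS.

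The planned comparator dose is "ibrutinib 420 mg QD (Arm B; N=250" (SAP 2.1). For reductions, Protocol Table 6-1 has acalabrutinib "restart at one dose level lower (100 mg once daily" at the third occurrence. Protocol Table 6-2 says ibrutinib "may restart at 280 mg daily" at the second occurrence and at 140 mg daily at the third.

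SAP 6.4 defines acalabrutinib dose reduction by its 100 mg once-daily level for at least 3 consecutive days, then adds: "For subjects randomized to ibrutinib, dose delay and modifications are defined the same as acalabrutinib".

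**The concern.** RDI is meant to express dose received as a share of dose planned. With acalabrutinib's 200 mg/day in the denominator for both drugs, it does that in one arm only. The same 75% rule then asks much more of acalabrutinib subjects than of ibrutinib subjects.

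In an open-label non-inferiority trial, a per-protocol analysis is read as a check on whether poor exposure has made the arms look alike in the ITT analysis. A post-randomization exclusion applied at different levels in the two arms selects different kinds of subjects from each. Neither agreement nor disagreement with the ITT result could then be read cleanly. The by-arm RDI table would also not be comparable between arms.

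**Working it through.** **Inputs.** RDI denominator: 200 mg per exposure day (SAP 6.3). Cut-off: 75% (SAP 3.3). Planned daily dose: acalabrutinib 2 × 100 = 200 mg, ibrutinib 420 mg (SAP 2.1). Reduced levels: acalabrutinib 100 mg/day (Protocol Table 6-1); ibrutinib 280 and 140 mg/day (Protocol Table 6-2).

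**Formula as written.** RDI = 100 × (mean daily dose) / 200.

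**Full dose.** Acalabrutinib: 200/200 = 100%, as it should be. Ibrutinib: 420/200 = 210%.

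**Where the cut falls.** 0.75 × 200 = 150 mg/day in both arms. As a share of plan, this is 150/200 = 75% for acalabrutinib and 150/420 = 35.7% for ibrutinib. On its own plan, ibrutinib's cut would be 0.75 × 420 = 315 mg/day. Ibrutinib subjects averaging from 150 to under 315 mg/day are therefore kept, while acalabrutinib subjects with the same relative under-dosing are removed. Ibrutinib subjects below 150 mg/day are still excluded, so the rule is unequal rather than one-sided.

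**Constant dose throughout.**

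| Mean daily dose | RDI as written | Share of own plan | As written | On own plan |
|---|---|---|---|---|
| Acalabrutinib 100 mg | 50% | 50% | excluded | excluded |
| Ibrutinib 280 mg | 140% | 66.7% | kept | excluded |
| Ibrutinib 140 mg | 70% | 33.3% | excluded | excluded |

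**Reduced for a fraction f of exposure, otherwise full dose.**

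- Acalabrutinib at 100 mg/day: 200 − 100f < 150, so f > 50%.
- Ibrutinib at 140 mg/day, as written: 420 − 280f < 150, so f > 96.4%. On its own plan: 420 − 280f < 315, so f > 37.5%.
- Ibrutinib at 280 mg/day, as written: never excluded. On its own plan: 420 − 140f < 315, so f > 75%.

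**Missed days at full dose.** Exclusion starts above 1 − 0.75 = 25% for acalabrutinib and above 1 − 150/420 = 64.3% for ibrutinib.

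**Possible effect on the per-protocol hazard ratio (hypothetical).** The documents do not say how many subjects will fall in the 35.7–75% band or how they will fare, so this step rests on assumptions. Trials were simulated with 250 per arm, analysis at 250 events, true HR 1.00, median PFS 36 months and accrual over 24 months (the plan's own values are redacted). A share of each arm was placed in the band and removed from the acalabrutinib arm only, and an unstratified Cox model was fitted. There were 2000 trials per scenario. Mean HR, acalabrutinib/ibrutinib:

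| PFS hazard of band vs rest | 3% in band | 5% | 10% | 20% |
|---|---|---|---|---|
| 0.7 | 1.01 | 1.01 | 1.03 | 1.07 |
| 1.0 | 0.99 | 1.00 | 1.00 | 1.00 |
| 1.5 | 0.99 | 0.98 | 0.96 | 0.92 |
| 2.0 | 0.98 | 0.96 | 0.93 | 0.86 |

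In a second set (1500 trials each), dose was halved at a random time unrelated to PFS, so that subjects who stay on drug longer are more likely to enter the band. With mean times to halving of 60, 100, 150 and 300 months, the mean HR was 1.15, 1.08, 1.06 and 1.03. The shift can go either way.

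**The case against.** The strongest reply is that this is a drafting omission. Relative dose intensity conventionally means relative to plan, and a programmer who saw 210% for every fully dosed ibrutinib subject would notice and use 420 mg. That may well happen, but neither document says so, and Protocol 9.1 requires changes to final SAP methods to be described and justified in the clinical study report. If the formula was meant for acalabrutinib alone, ibrutinib has no defined RDI and the 75% rule cannot be applied to that arm. Under either reading the text needs correcting.

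Second, RDI mixes non-adherence with reductions that the protocol directs, and the reduction schedules differ by arm. An ibrutinib subject at 280 mg/day for more than 75% of exposure would be excluded under a 420 mg denominator despite following the protocol. This stands: an arm-specific denominator equalises the percentage cut-off but does not make the two per-protocol sets fully comparable on adherence.

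Third, the simulated figures depend on assumed inputs, including equal prevalence in both arms. At 3–5% prevalence the mean HR stays between 0.96 and 1.01, and the larger shifts come from the extreme scenarios. This also stands. The figures show sensitivity to assumptions, not an expected bias.

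Fourth, the per-protocol analysis carries no decision rule, and RDI is one of three exclusions. True, which limits the consequence.

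On SAP 6.4, a reader would probably carry over only the idea of a lower dose level for at least 3 days, since 100 mg is not an ibrutinib level. That wording is a secondary clarification.

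**Conclusion.** The concern holds. Followed exactly, SAP 6.3 misstates RDI for the whole ibrutinib arm, and SAP 3.3 then excludes at 75% of plan in one arm and 35.7% in the other. These figures follow from the documents alone. The size and sign of any effect on the per-protocol hazard ratio do not: they depend on how many subjects are under-dosed in each arm and on whether low RDI goes with worse PFS or with longer time on drug.

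The damage is confined to the exposure table and the per-protocol sensitivity analysis. Non-inferiority rests on the ITT analysis against 1.429, which is untouched, as are the event count, power and gatekeeping. The point should be fixed but does not threaten the primary conclusion.

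**What to change.** - **SAP 6.3:** define RDI as 100 × cumulative dose / (exposure days × planned daily dose of the arm), with 200 mg for acalabrutinib and 420 mg for ibrutinib, the doses already stated in SAP 2.1.
- **SAP 3.3:** state that the 75% rule refers to this arm-specific RDI.
- **SAP 6.4 (clarification):** define ibrutinib dose reduction as a dose below its own planned level for at least 3 consecutive days, so that the 100 mg once-daily level is not carried over.

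These are analysis definitions only; no dose or clinical rule changes. The cost is one formula line, one cross-reference, one phrase and a small programming change. No new data are needed. Making the change before database lock and unblinding avoids any appearance of a choice made after seeing results.

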### 6.4 Study Treatment Modifications

For subjects randomized to acalabrutinib arm, acalabrutinib dose withholding is defined as missing dose for  $\geq 7$  consecutive days, and acalabrutinib dose reduction is defined as taking lower dose level (100 mg QD) for  $\geq 3$  consecutive days. Subjects with dose withholding and reduction will be summarized by percent of subjects as well as descriptive statistics.

For subjects randomized to ibrutinib, dose delay and modifications are defined the same as acalabrutinib and will be summarized by percentage of subjects and by descriptive statistics.

## 7 EFFICACY ANALYSES

All efficacy analyses will be performed at the 2-sided significance level. Analyses will be based on the ITT population, and subjects will be analyzed according to the randomized treatment, unless otherwise specified.

The following three randomization stratification factors (collected via IWRS) will be used for the stratified analyses: presence of 17p del (yes, no), ECOG status (2 vs.  $\leq 1$ ), and number of prior therapies (1–3 vs.  $\geq 4$ ). For the primary efficacy analysis of IRC-assessed PFS, if there is at least one stratum that has fewer than 2 events (where a stratum is defined as stratification factor 1 \* stratification factor 2 \* stratification factor 3), stratification factors should be collapsed until all strata have at minimum 2 events for the primary endpoint. The stratification factors will be collapsed in the following order:

1. ECOG status (2 vs.  $\leq 1$ )
2. Presence of 17p del (yes vs. no)

If there is still at least one stratum that has fewer than 2 events after collapsing the 2 stratification factors above, an unstratified analysis (equivalently as to collapse all 3 stratification factors) will be performed as the primary analysis.

All stratified analyses will be conducted in accordance with this prespecified pooling strategy as above stated for the primary analysis of PFS.

## 7.1 Primary Efficacy Endpoint and Analysis

### 7.1.1 Primary Efficacy Endpoint

The primary efficacy endpoint is PFS as assessed by IRC, defined as the time from date of randomization to the date of first IRC-assessed disease progression or death due to any cause.

Subjects who do not have an IRC confirmed disease progression or death at or prior to data analysis cutoff date will be censored as follows:

**Table 2.** Primary Efficacy Analysis of PFS-IRC Outcome

Situation	Date of Event or Censoring	Outcome
Situation 1: PFS events include death or first IRC-confirmed disease progression that occurred at or prior to the data analysis cutoff date. Date of event is defined as follows:		
Death before first disease assessment	Date of death	Event
IRC-confirmed PD or death between scheduled assessments	Earliest date of IRC confirmed PD or death	Event
Situation 2: All other cases not meeting Situation 1 will be censored as follows:		
No baseline assessments	Randomization	Censored
No adequate post-baseline assessment	Randomization	Censored
No IRC-confirmed PD or death at the time of data cutoff	Date of last adequate IRC assessment before data cutoff	Censored
No IRC-confirmed PD or death before lost to follow-up or study exit	Date of last adequate IRC assessment before lost to follow-up or study exit	Censored
No IRC-assessed PD or death before start of subsequent anticancer therapy	Date of the last adequate IRC assessment before start of subsequent anticancer therapy	Censored

Situation	Date of Event or Censoring	Outcome
IRC-assessed PD or death after start of subsequent anticancer therapy	Date of the last adequate IRC assessment before start of subsequent anticancer therapy	Censored
IRC-confirmed PD or death immediately after 2 or more consecutively missed visits	Date of last adequate IRC assessment before the consecutively missed visits	Censored

PD=progressive disease; IRC=independent review committee.

PFS will be calculated as date of disease progression or death (censoring date for censored subjects) – randomization date + 1.

The adequate IRC assessment is defined as the IRC-assessed overall response that is not 'UNK' (unknown), as defined in the IRC charter.

